4.1.2. Exclusion Criteria

1. Diagnosis of acute promyelocytic leukemia.

2. Chronic myeloid leukemia in blast crisis (positive for a breakpoint cluster region-c-Abelson [BCR-ABL] fusion gene).
3. History of or concurrent central nervous system leukemia.
4. History of hematopoietic stem cell transplant (HSCT) and meeting any of the following:
 - i) Transplantation within 60 days before the start of study treatment
 - ii) Persistent graft-versus-host disease (GVHD) that is clinically significant, requires the start of treatment, or requires intensification of treatment within 21 days before informed consent
 - iii) Persistent Grade ≥ 2 clinically significant or irreversible non-hematological toxicity related to transplantation
5. Uncontrolled infection requiring intravenous antibiotics, antifungals, or antivirals.
6. A positive test result for hepatitis C virus (HCV) antibody or human immunodeficiency virus (HIV) antibody within 90 days before enrollment.
7. A positive test result for hepatitis B surface (HBs) antigen within 90 days before enrollment.
8. A positive test result for hepatitis B core (HBc) antibody or HBs antibody with hepatitis B virus (HBV)-DNA levels ≥ 2.1 log copies/mL, despite a negative test result for HBs antigen, within 90 days before enrollment.
9. Receiving strong CYP3A inhibitors within 7 days before the start of study treatment.
10. Receiving strong CYP3A inducers within 14 days before the start of study treatment.
11. History of or current cardiovascular disease as specified below:
 - i) QT corrected for heart rate using Fridericia's method (QTcF) interval >450 ms, determined as the average of triplicate ECG measurements taken within 14 days before enrollment in this study
 - ii) Class III or more severe congestive heart failure according to "[Appendix 3](#) New York Heart Association (NYHA) Functional Classification" within 6 months before enrollment in this study
 - iii) History of myocardial infarction within 6 months before enrollment in this study
 - iv) History of angina pectoris attack within 6 months before enrollment in this study
 - v) History of arrhythmia requiring treatment within 6 months before enrollment in this study
 - vi) Need for a pacemaker or implantable cardioverter defibrillator
 - vii) Diagnosed or suspected congenital long QT syndrome

- viii) History of life-threatening ventricular arrhythmia (ventricular tachycardia, ventricular fibrillation, or torsades de pointes)
- ix) History of bradyarrhythmia (eg, atrioventricular block)
- x) Clinically significant electrolyte abnormalities that can induce secondary long QT syndrome
- xi) Uncontrolled hypertension despite pharmacotherapy etc.

12. Adverse drug reactions (excluding alopecia) to previous therapy (treatment for AML and/or anticancer therapy), which have not resolved or returned to Grade 1 or baseline. Patients with chronic Grade 2 adverse drug reactions (eg, chemotherapy-induced neuropathy) may be eligible when the investigator or subinvestigator decides that there are no clinical safety concerns from the standpoint of the patient's safety.

* The grade will be assessed according to the "Common Terminology Criteria for Adverse Events (CTCAE) Version 5.0."

13. History of another malignant tumor requiring treatment within 2 years before enrollment in this study.

However, patients whose disease is considered to have been cured by local treatment (eg, non-melanoma skin cancer, superficial bladder cancer, or carcinoma in situ of the cervix or breast) may be eligible for participation in the study.

- 14. Predisposition to serious infection (eg, cystic fibrosis, congenital or acquired immunologic disease, hemorrhagic disease, or cytopenia unrelated to AML).
- 15. Disseminated intravascular coagulation or other clinically significant coagulation abnormalities.
- 16. Extensive surgery within 28 days before the start of study treatment.
- 17. Radiation therapy within 28 days before the start of study treatment.
- 18. Any factor that could preclude adequate absorption of DS-3032b (eg, refractory nausea and vomiting, malabsorption, biliary shunt, significant bowel resection, and/or GVHD affecting the gut).
- 19. Pregnant or breastfeeding women.
- 20. Patients who are otherwise considered ineligible for the study in the opinion of the investigator or subinvestigator.

Rationale:

- 1 to 18. To appropriately evaluate the safety of DS-3032b.
- 19. Since an effect of DS-3032b on fetuses or infants cannot be ruled out. Breastfeeding women are not allowed to participate in this study independent of whether or not they temporarily discontinue breastfeeding.

20. To allow the investigator or subinvestigator to determine the subject's eligibility for participation in the study from a comprehensive standpoint, including careful consideration of the subject's safety.

4.1.3. Registration of Subjects

Subjects will be registered in the study according to the procedure described below.

4.1.3.1. Flow of Subject Registration

After obtaining written informed consent from subjects, the investigator or subinvestigator will assign a subject identification code to each of the subjects. The investigator or subinvestigator will fill out the Subject Registration Form for subjects who are assessed to be eligible for the study among the above subjects and send it by fax to the sponsor.

The sponsor will confirm the eligibility of the concerned subjects against the inclusion and exclusion criteria for this study based on the information in the received Subject Registration Form. If there are any questions about the information in the Subject Registration Form, the sponsor will immediately contact the investigator or subinvestigator for confirmation. Subjects who are assessed to be eligible for the study by the sponsor will be registered in this study and assigned a subject number.

The sponsor will immediately fax the registration confirmation form with the result of eligibility assessment to the investigator; the confirmation form should include the date of registration, subject number, and dose of the study drug for subjects assessed to be eligible, and the fact that the subject is not eligible and the reason for subjects assessed to be ineligible. The investigator or subinvestigator will explain the reason for ineligibility to subjects who are assessed to be ineligible for the study by the sponsor.

Address for sending the Subject Registration Form (the sponsor's address)

Working hours: Monday to Friday, 9:00 to 17:30
(closed on Saturdays, Sundays, and public holidays)

FAX: PPD

TEL: PPD

[figure not shown]
The investigator or subinvestigator must not prescribe the study drug before registration of subjects.

If there is any subject who has provided informed consent, but is not registered in the study, the investigator or subinvestigator will record the reason why the concerned subject has not been registered in the medical record. Such a subject will not be included in the number of subjects enrolled in this study.

If a subject who has provided informed consent, but is assessed to be ineligible for the study at the time of eligibility confirmation and for whom a Subject Registration Form has not been faxed to the sponsor, is confirmed to satisfy the eligibility criteria at a later date, the investigator or subinvestigator may fax the Subject Registration Form to the

sponsor after re-obtaining written informed consent to participate in this study from the concerned subject.

Figure 4.1-1: Subject Registration Procedure

4.1.3.2. Notifying Any Other Physicians Treating Subjects of Their Study Participation

The investigator or subinvestigator will ask subjects who have provided informed consent whether they are being treated by another physician (eg, a physician in another department of the study center or at another medical institution) or not. If the subject is receiving treatment by another physician, the investigator or subinvestigator will inform the physician of the subject's participation in the study with the subject's approval and record the information in the medical record.

4.2. Subject Withdrawal Criteria and Procedure at Withdrawal

If a subject meets “Section 5.6 Withdrawal Criteria” while participating in this study, the investigator or subinvestigator will discontinue the study treatment for the concerned subject, and perform the examinations and assessments in accordance with “Section 6.4 Procedures at Study Discontinuation.” The investigator or subinvestigator will record the date of discontinuation, reason for discontinuation, examination and investigation results in the case report form.

5. METHODOLOGY

5.1. Study Drug

For the details of the study drug and its handling, see the “Investigator’s Brochure” and “Procedure for Study Drug Management.”

1. Investigational substance code: DS-3032b
2. Generic name: milademetan
3. Content and dosage form:

White opaque capsules, each of which contains 30 mg of DS-3032b as the free form of its drug substance, or white opaque, red-lined capsules, each of which contains 100 mg of DS-3032b as the free form of its drug substance.

4. Lot number: Lot numbers are listed in the “Procedure for Study Drug Management.”

5.1.1. Labeling and Packaging

Thirty five capsules of the study drug are packed with a desiccant agent in a plastic bottle. The information that should be included on the label is provided in [Table 5.1.1 Descriptions on the Labeling of the Study Drug](#).

Table 5.1.1: Descriptions on the Labeling of the Study Drug

Labeled as “For Clinical Trial Use Only”
Study drug name
Protocol number
Study drug lot number
Storage conditions
Statement, “Do not discard but store unused study drug tablets; they will be collected later.”
Name of the sponsor
Address of the sponsor

5.1.2. Storage of the Study Drug

After concluding the clinical study contract, the sponsor will distribute the study drug to the study center. The study drug manager will store and manage the study drugs, which are placed with a desiccant agent in plastic bottles, at up to 25°C (excursions permitted up to 30°C). The study drug will be managed and collected in accordance with the “Procedure for Study Drug Management.”

5.2. Method of Study Treatment

5.2.1. Dose

The starting dose of DS-3032b in Subtrial A will be 90 mg. The subsequent doses will be determined, taking the following into consideration.

- i) Recommended dose, guided by mCRM using a BLRM incorporating the EWOC principle
- ii) Clinical evaluation of the toxicological profile and information on PK/PD_y

Dose increments should be at least 1.3-fold in order to make a distinction among the dose cohorts, considering inter-subject variability in exposure. Even if the recommended dose for the next cohort calculated by the model is more than 2-fold, the dose should be no more than 2-fold.

5.2.2. Regimen

In Subtrial A, the study drug will be administered once daily on Days 1 to 14, followed by a 14-day rest, in a 28-day cycle (14/28 schedule). Each cycle is 28 days long.

[figure not shown]
Capsules with two different strengths will be used as the study drug (30 mg and 100 mg). As a rule, subjects will orally take the study drug once daily every morning under fasting conditions. Meal consumption should be avoided from 2 hours before dosing to 1 hour after dosing.

The first dose of the study drug will be started within 7 days of the day of registration. If the study treatment is started on Day 8 or later from the day of registration, the first dose of the study drug should be started only after the subject's eligibility has been confirmed again before the start of the study treatment (see "[Section 6.2 Study Procedures before Registration of Subjects](#)"). Day 1 of Cycle 3 and subsequent cycles may be rescheduled within + 3 days of the originally scheduled date. If the schedule of Day 1 is changed, all subsequent scheduled dates will be changed accordingly.

If a subject vomits after taking the study drug, it is not allowed to take another dose of the study drug on the same day.

Other dosing schedules (Subtrials B, C, and D) will be assessed if it becomes necessary in order to evaluate the safety of DS-3032b. Dosing schedules in each subtrial are shown in "[Figure 5.2-1 Dosing Schedules in Each Subtrial](#)."

Figure 5.2-1: Dosing Schedules in Each Subtrial

5.2.3. Rationale for the Dose and Regimen

The dose and regimen of this study were established in reference to the results of the Phase 1 studies that are currently underway in the US and Japan. In DS3032-A-J103, a Japanese study of DS-3032b in subjects with solid tumors or lymphomas, the MTD was determined to be the 90 mg qd 21/28 day schedule. Based on this result, the starting dose for this study was determined to be 90 mg/day once daily. In DS3032-A-U102, an overseas study of DS-3032b in subjects with hematological malignant tumors, CR as determined by bone marrow assessment was achieved in 1 subject with high-risk MDS treated on the 160 mg qd 14/28 day schedule. The 14/28 day schedule is also adopted in another overseas clinical study that is currently underway. It was therefore considered appropriate to start the treatment on the 14/28 day schedule in this study. The study was designed to increase the dose based on the recommended dose guided by mCRM, with the planned maximum dose of 160 mg/day.

5.2.4. Randomization and Blinding

No randomization or blinding will be performed in this study.

5.3. Definition of Dose-limiting Toxicities and Maximum Tolerated Dose

5.3.1. Definition of Dose-limiting Toxicities

A DLT is defined as any Grade 3 or higher non-hematological AE unless related to the primary disease, course of the primary disease, complications, or concomitant medications, that occurs during the DLT evaluation period (28 days of Cycle 1), with the exceptions as defined below:

1. The following events will be assessed as DLTs:
 - Grade 4 aspartate aminotransferase (AST)/alanine aminotransferase (ALT)

- Grade 3 AST/ALT lasting ≥ 3 days, Grade 3 AST/ALT with Grade ≥ 2 total bilirubin
- Unable to complete at least 75% of the prescribed doses of DS-3032b in Cycle 1 (28 days) as a result of Grade ≥ 2 events

2. The following events will not be assessed as DLTs:

- Grade 3 fatigue lasting < 3 days
- Grade 3 nausea or vomiting that has resolved to Grade ≤ 2 within 48 hours after antiemetic therapy
- Grade 3 diarrhea that has resolved to Grade ≤ 2 within 48 hours after antidiarrheal therapy
- Alopecia
- Febrile neutropenia
- Transient laboratory abnormalities that do not involve clinical symptoms and do not require continuous treatment (\geq Grade 3 ALP, uric acid, amylase, and lipase, hyponatremia that has resolved within 72 hours after onset, etc.)

The following hematological toxicities will be assessed as DLTs.

- Failure to recover neutrophil count to $\geq 500 /mm^3$ and platelet count to $\geq 20,000 /mm^3$, leading to a delay in starting Cycle 2 for more than 2 weeks

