1.3. Summary of Significant Findings Obtained from Previous Clinical Studies

1.3.1. Overseas Phase 1 Studies (Study DS3032-A-U101 and Study DS3032-A-U102)

DS3032-A-U101 is a Phase 1, multicenter, open-label study of DS-3032b in subjects with solid tumors or lymphomas, which are refractory to standard therapies or for which no standard treatment is available. This study consists of Part 1 (dose escalation) and Part 2 (dose expansion). The objectives of Part 1 were to evaluate the safety and tolerability of DS-3032b and assess the maximum tolerated dose (MTD) or the recommended phase 2 dose (RP2D) of DS-3032b. The objectives of Part 2 were to evaluate preliminary tumor response in subjects with advanced melanoma and subjects with diffuse large B-cell lymphoma (DLBCL). As of 31 Oct 2016, 69 subjects have been treated with DS-3032b in this study (49 subjects in the dose escalation part [Part 1] and 20 subjects in the dose expansion part [Part 2]), and 9 subjects are ongoing in the study. In Part 1, DS-3032b was administered once daily on Days 1 to 21, followed by a 7-day rest, in a 28-day cycle (qd 21/28 day schedule), starting from 15 mg and escalating through 30, 60, 120, 160 and 240 mg, guided by a modified continual reassessment method (mCRM) incorporating the escalation with overdose control (EWOC) principle. Dose-limiting toxicities (DLTs) were reported as Grade 4 thrombocytopenia and Grade 4 febrile neutropenia in 1 subject treated at 240 mg, and the study was continued at a reduced dose of 160 mg. At 160 mg, DLTs were reported as Grade 3 anorexia, nausea, and vomiting in 1 subject and Grade 4 neutropenia and Grade 2 thrombocytopenia in 1 subject. As a result, the study was continued at a further reduced dose of 120 mg. At

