5.3.2. Definition of Maximum Tolerated Dose

If any of the following completion criteria are met, the MTD will be determined based on comprehensive evaluation of the recommended dose guided by mCRM incorporating the EWOC principle, and safety and PK/PDy information of DS-3032b.

Completion criteria:

- DLT evaluation is completed in at least 15 subjects in the entire study and in at least 6 subjects in the cohort of the dose selected to be the dose for the next cohort by mCRM.
- DLT evaluation is completed in at least 6 subjects in the cohort of the dose selected to be the dose for the next cohort by mCRM, with at least 50% posterior probability for the DLT rate ranging between 16% and 33%.
- DLT evaluation is completed in at least 3 subjects in the cohort of each dose, with no DLTs reported.
- The posterior probability for the DLT rate of 33% or higher in the 90 mg cohort is at least 60%.

5.3.3. Study Treatment to Subjects in Each Cohort and Procedure for Proceeding to the Next Cohort

In the cohort of the first dose, study treatment for the second subject must be started after an at least 1-week interval from the first dose of treatment in the first subject. In the subsequent cohorts, study treatment for the next subject may be started on the following day of the start day of study treatment in the first subject.

If proceeding to the next cohort involves an increase in the dose, study treatment for the first subject in the new cohort will be started after the end of the DLT evaluation period in at least 3 subjects in the ongoing cohort. If a DLT occurs in 2 subjects before registration of the third subject, the dose for the third subject will be reviewed by using the mCRM incorporating the EWOC principle.

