11.2.2. Maximum Tolerated Dose Analysis Set

The MTD analysis set will include all subjects who received at least one dose of the study drug but will exclude subjects who have missing data of one or more examination or observation items during the DLT evaluation period for other reasons than adverse drug reactions (worsening of clinical conditions due to progression of the primary disease, AEs for which a relationship with the study drug is ruled out, etc.) and whose DLT evaluation could not be performed appropriately. The MTD analysis set will also include subjects who have experienced DLT in Cycle 1 and subjects who have received the study drug on at least 75% of the specified days in Cycle 1 in the absence of DLT.

Subjects for whom the study treatment is postponed due to a DLT occurring during the DLT evaluation period, and the study treatment is then resumed at a reduced dose will be

handled as those included in the MTD analysis set for the dose level at the first dose of the study drug.

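### A drug-related death recorded as febrile neutropenia late in Cycle 1 meets no DLT line, so the count behind escalation and study completion can miss it

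*Combined protocol and SAP*

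**What the plan says.** The base rule in protocol Section 5.3.1 reads: "A DLT is defined as any Grade 3 or higher non-hematological AE unless related to the primary disease". It goes on to exclude events related to the course of the disease, complications or concomitant medications, and it covers the 28 days of Cycle 1. The second list, headed "The following events will not be assessed as DLTs", contains the bare entry "Febrile neutropenia". Its neighbours are bounded. The fatigue entry begins "Grade 3 fatigue lasting" and is limited to under 3 days; the nausea/vomiting and diarrhea entries are limited to Grade 3 with recovery within 48 hours of treatment.

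Two other lines in 5.3.1 could still catch a febrile neutropenia case. One is failure to complete 75% of Cycle 1 doses because of Grade 2 or higher events. The other, the only hematological DLT, is non-recovery of neutrophils and platelets that delays Cycle 2 by more than 2 weeks.

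Section 11.2.2 puts into the MTD analysis set "subjects who have received the study drug on at least 75% of the specified days in Cycle 1 in the absence of DLT". The third completion criterion in Section 5.3.2 is: "DLT evaluation is completed in at least 3 subjects in the cohort of each dose, with no DLTs reported".

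**The concern.** The severity scale in Section 9.3 runs to Grade 5, death. An exemption without an outcome limit therefore reaches a fatal event. Disease-related events already fall outside the base rule, so what matters here is a death attributed to DS-3032b. Sections 1.2.4 and 1.4 describe bone marrow suppression as a principal effect in dogs, so the event is not fanciful.

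If such a death is scored as no DLT, the data given to the Bayesian logistic regression model understate toxicity at that dose, and the no-DLT completion criterion can be met with a treatment-related death in the cohort. The score would also turn on the recorded term. Section 9.3 merges correlated signs into one diagnosis. Recorded as sepsis, the death is a Grade 5 non-hematological event and a DLT; recorded as febrile neutropenia, it is not.

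**Working it through.** **Does any DLT line catch the case?** Subtrial A doses on Days 1 to 14 of a 28-day evaluation period (Sections 5.2.2 and 5.3.1).

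- Missed doses: 0.75 × 14 = 10.5, so 11 doses satisfy the rule. With uninterrupted dosing, a fatal case from Day 12 to Day 28 does not meet this line.
- Cycle 2 delay: the rule presupposes a Cycle 2 that starts late. After a death there is none.
- Base rule: if febrile neutropenia is non-hematological, the second list exempts it. If it is hematological, the base rule never reaches it. Neither classification gives a DLT.
- Analysis set: the missing-data exclusion in 11.2.2 applies only to reasons other than adverse drug reactions, so it does not remove a drug-related death. Section 5.4 replaces subjects not evaluable because of withdrawal, but 5.6 does not name death among the withdrawal reasons. Even if the subject is replaced, no DLT is recorded.

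**Reproducing the plan's figures.** Sections 11.7.1 and 11.7.2 give logit π(d) = log α + β log(d/160), with (log α, log β) bivariate normal: means (−1.8999, 1.3484), SDs (2.2792, 1.3727), correlation −0.3157. At 160 mg the prior median is 1/(1 + e^1.8999) = 13.0%. Integration over a grid gives 3.06% at 120 mg. These match the stated 13% and 3%. The minimum sample size in Section 11.6 is 3 × 3 = 9.

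**Effect of scoring one case.** The posterior is proportional to the prior times the product over doses of π(d)^x (1 − π(d))^(n−x), for x DLTs in n subjects. Candidates are the planned doses. The 25% in Section 11.7.3 is read as a ceiling on P(DLT rate >33%); overdose control applies because the next cohort is the third or later. Target means a DLT rate above 16% and up to 33%. Values move only slightly, in the third decimal, with grid spacing.

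| DLTs at 90, 120, 160 mg | P(>33%) at 120 mg | P(>33%) at 160 mg | P(target) at 120 mg | P(target) at 160 mg | Model's choice |
|---|---|---|---|---|---|
| 0/3, 0/3, none yet (case exempt) | 0.01 | 0.11 | 0.04 | 0.15 | 160 mg |
| 0/3, 1/3, none yet (case counted) | 0.15 | 0.44 | 0.30 | 0.29 | 120 mg |
| 0/3, 0/3, 0/3 (case exempt) | <0.01 | 0.02 | 0.02 | 0.09 | 160 mg |
| 0/3, 0/3, 1/3 (case counted) | 0.01 | 0.21 | 0.09 | 0.32 | 160 mg |

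For a case at 120 mg the recommendation changes. For a case at 160 mg it does not: 0.21 is under 25%, and 160 mg has the highest target probability. What changes there is completion. Scored 0/3, the third criterion is met at 9 evaluated subjects. Scored 1/3, it is not, and the first two criteria need at least 6 subjects at the selected dose, that is 6 − 3 = 3 more.

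**Frequency.** Section 1.4 reports febrile neutropenia in 6/37 = 16.2% of U102 subjects, with no grade, cycle or relation to drug. No rate of drug-related fatal cases is given. Purely as assumptions, per-subject rates of 2% and 5% give a chance of at least one in 9 of 1 − 0.98^9 = 16.6% and 1 − 0.95^9 = 37.0%.

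**The case against.** The strongest reply is that the exemption fits a deliberate AML definition. This protocol does not count cytopenias by grade, and if febrile neutropenia is hematological the entry merely clarifies. U102, the study in hematological malignancies, had febrile neutropenia in 6/37 subjects and none among its listed DLTs. This stands for non-fatal cases, and the plan should not be faulted for exempting them. It does not explain why a drug-related death should go uncounted.

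A reader might infer that this plan contradicts U101, which reported as DLTs "Grade 4 thrombocytopenia and Grade 4 febrile neutropenia in 1 subject treated at 240 mg". The documents do not support that. U101 enrolled solid tumors and lymphomas and counted cytopenias by grade; that subject also had Grade 4 thrombocytopenia, at a dose above this study's planned maximum of 160 mg.

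A reader might also infer that all life-threatening febrile neutropenia is scored DLT-free. It is not. A survivor whose counts delay Cycle 2 by more than 2 weeks, a subject who cannot complete 75% of doses because of the event, and a separately diagnosed drug-related Grade 3 or higher infection outside the exemptions all remain DLTs.

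Nor does the plan declare an MTD automatically. Sections 3.2 and 5.3.2 require clinical evaluation alongside the model, and Section 15.9 allows the sponsor to halt on serious adverse event information. A treatment-related death would very probably prompt that review. These safeguards are real but discretionary, and none corrects the count used by the model or by the third criterion.

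Finally, the posterior shifts are not specific to febrile neutropenia: any case moved from 0/3 to 1/3 gives them. That is accepted; they measure what one unscored case does.

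**Conclusion.** The gap is real but narrow. It concerns a death during Cycle 1, attributed to DS-3032b, recorded as febrile neutropenia, after at least 11 of 14 doses in Subtrial A. Followed literally, the plan leaves that death out of the DLT count.

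If it falls in the 120 mg cohort after 0/3 at 90 mg, the model would recommend 160 mg where it would otherwise recommend 120 mg. If it falls in the 160 mg cohort after two clean cohorts, only the third completion criterion is affected.

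These results rest on cohorts of 3, the planned doses only, and 25% read as a ceiling. Without the ceiling, 120 mg still leads in the first scenario, but only by 0.30 to 0.29. How often the event would occur cannot be judged from the documents. The change is worth making because it is cheap and protects the primary objective, not because the event is shown to be likely.

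**What to change.** State in Section 5.3.1 that neither the second-list exemptions nor the split between hematological and non-hematological events removes from the DLT count a death in the DLT evaluation period that is not attributed to the primary disease, its course, complications or concomitant medications. Naming the split makes the sentence work however febrile neutropenia is classed. Then reconcile 5.3.1 with 5.3.2, 5.4 and 11.2.2 so that all four say the same about scoring a Cycle 1 death.

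Whether non-fatal febrile neutropenia stays exempt is for the sponsor's clinicians; no grade or duration limit is proposed here.

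The cost is one sentence plus the cross-checks. The downside is that a rare event now counts, and may slow escalation or take the study beyond 9 subjects.
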